### **11.3 Interim analyses**

We will evaluate if Ga-NeoBOMB1 and Ga-PSMA R2 will have the same findings as what was noted with Ga68 PSMA-11 and Ga68 RM2 (bombesin), ie, about 2/3 same findings, while 1/3 will show different findings. We will do the interim analysis after enrollment of 20 participants. If all participants will have the same findings or if one

radiopharmaceutical will outperform the other (no additional lesions found by one vs another), the study will be discontinued.

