## **10. MEASUREMENTS**

### **10.1 Primary outcome measure**

The principal goal of this study is to compare the diagnostic performance of Ga-NeoBOMB1 PET/MRI and Ga-PSMA R2 PET/MRI to that of MR alone in clinically (PSA) recurrent but CT-negative prostate cancer patients. The gold standard will be based on either biopsy or one-year follow-up with imaging.

Specifically, it is expected that:

1. At least 30% of these patients will have one or more lesions detected on Ga-NeoBOMB1 PET/MRI or Ga-PSMA R2 PET/MRI.
2. The proportion of patients with detected lesions will be higher for Ga-NeoBOMB1 PET/MRI or Ga-PSMA R2 PET/MRI than for MR alone.
  - Primary Outcome measure: Number of lesions detected by investigational imaging agent
  - Timeframe: Within 30 days
  - Description: The number of lesions detected on Ga- NeoBOMB1 PET/MRI, Ga-PSMA R2 PET/MRI, and conventional MR will be compared. Outcome will be reported as number of lesions detected per patient for each imaging method.

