##### **11.4.2 Analysis Plan**

- Sensitivity, specificity, and positive and negative predictive value of imaging modalities will be estimated.
- Sensitivity and specificity of PET/MRI and MR alone will be compared by McNemar tests of paired proportions.
- The number and type of discrepancies between  $^{68}\text{Ga}$ -NeoBOMB1 and  $^{68}\text{Ga}$ -PSMA R2 will be tabulated.
- We will explore hypotheses about the reasons for such discrepancies, such as PSA level/velocity, Gleason score, and location.

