#### **11.5 Sample size justification**

The following estimate is for a per-lesion analysis. We expect approximately 70% of patients (~35) to have one or more PET-positive findings and approximately 1/3 to be biopsied. Our existing data for  $^{68}\text{Ga}$  PSMA-11 and  $^{68}\text{Ga}$ -RM2 (please see attached publications) indicate no false positive findings based on biopsy. We cannot predict an average number of lesions per patient given small data available to date, but if only half of the positive patients have more than one lesion, this will easily yield 50 lesions. We also expect the sensitivity of MR alone to be roughly 40%, while that of PET to be roughly 60% or more. A sample size of 50 patients will provide 90% power at one-sided 5% error to detect such a difference. Participants who complete only one PET/MRI scan (either due to withdrawal of consent or loss to follow-up) will not be replaced with additional subjects.

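### The interim rule can end the whole study at 20 of 50 participants on a tracer-versus-tracer result, although the principal goal, the only named test and the 90% power concern PET/MRI versus MR alone

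*Combined protocol and SAP*

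**What the plan says.** Section 11.3 fixes the timing: "We will do the interim analysis after enrollment of 20 participants". It expects the two tracers to behave like two earlier agents, with "about 2/3 same findings, while 1/3 will show different findings". There are two triggers. The first is that every participant has the same findings on both tracers. The second is that one "radiopharmaceutical will outperform the other (no additional lesions found by one vs another), the study will be discontinued". Both lead to discontinuation of the study as a whole, and neither refers to MR.

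Section 10.1 states the principal goal as comparing the diagnostic performance of each tracer's PET/MRI "to that of MR alone in clinically (PSA) recurrent but CT-negative prostate cancer patients". Its primary outcome description also sets the two tracers and conventional MR beside each other: "Outcome will be reported as number of lesions detected per patient for each imaging method".

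Section 11.4.2 names one test: "Sensitivity and specificity of PET/MRI and MR alone will be compared by McNemar tests of paired proportions". For the tracers against each other it plans only a table and exploration: "The number and type of discrepancies between" the two agents are counted, and possible reasons are explored.

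Section 11.5 expects a sensitivity of roughly 40% for MR and 60% or more for PET, and concludes: "A sample size of 50 patients will provide 90% power at one-sided 5% error to detect such a difference". It does not mention the interim look.

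**The concern.** The stopping rule and the powered objective concern different comparisons. Two tracers that agree completely, or one that adds nothing to the other, tell us nothing about whether either is better than MR. Followed literally, 11.3 ends the trial in those situations even if PET/MRI is clearly ahead of MR. The question that sized the study would then be left with 40% of its planned participants (20/50). The 90% in 11.5 assumes that all 50 are always reached.

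The second trigger also needs one meaning. The bracket most naturally says that one tracer finds no lesion that the other misses. It gives no unit (patient or lesion), and it could be taken to mean that neither tracer adds anything, which would only repeat the first trigger. A decision that ends the study should not depend on a reading chosen after the data have been seen.

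**Working it through.** **Inputs from the plan.** Look at 20 of 50 participants and 1/3 with different findings (11.3); sensitivity 40% versus 60%, one-sided 5%, 90% power, about 50 lesions, about 70% of patients PET-positive (11.5); McNemar test (11.4.2).

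**Assumptions, because the plan is silent.** The 1/3 is per patient; each discordant patient has extra lesions on one tracer only; the split between tracers is even unless stated; lesions are independent; the McNemar discordance is as shown.

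**Step 1: the plan's 90%.** Let ψ be the share of lesions on which PET and MR disagree. The difference is 0.60 − 0.40 = 0.20. The normal approximation is

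power = Φ[(0.20·√n − 1.645·√ψ) / √(ψ − 0.20²)].

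At n = 50 this gives 90% when ψ ≈ 0.25 (more exactly 0.251). The exact McNemar test gives 88% there. So 90% is reproduced, but only at a discordance that the plan does not state.

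**Step 2: power if the study stops.** Scaling 11.5's lesion count, 50 × 20/50 = 20 lesions.

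| Lesions | ψ | Normal | Exact |
|---|---|---|---|
| 50 | 0.25 | 90% | 88% |
| 20 | 0.20 | 65% | 37% |
| 20 | 0.25 | 56% | 34% |
| 20 | 0.52 (independent readings) | 34% | 23% |

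Twenty lesions is towards the low end, since 11.5 regards 50 as easily reached. With 30 lesions at ψ ≈ 0.25, power would be 72% (normal) or 61% (exact).

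**Step 3: chance of stopping on the natural reading.** Let a and b be the probabilities that a patient has extra lesions on the first or the second tracer. The study stops if either kind is absent from all 20 patients:

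P(stop) = (1 − a)^20 + (1 − b)^20 − (1 − a − b)^20.

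The last term is the overlap in which all findings agree.

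- Even split, a = b = 1/6: 0.0261 + 0.0261 − 0.0003 = 0.052.
- 80:20 split, a = 0.267, b = 0.067: 0.0020 + 0.2516 − 0.0003 = 0.253.
- The 1/3 applied only to the 70% who are PET-positive, a + b = 0.70/3 = 0.233, even split: 0.0837 + 0.0837 − 0.0049 = 0.162.
- A quarter of discordant patients with extra lesions on both tracers (1/12 of all patients), the rest split evenly (a = b = 1/8): 2 × (1 − 1/8 − 1/12)^20 − (2/3)^20 = 0.018.

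The first trigger alone has probability (2/3)^20 = 0.0003.

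**Step 4: overall power.** If stopping is independent of the MR comparison, overall power = (1 − P(stop)) × power at 50 + P(stop) × power at 20, with ψ ≈ 0.25.

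- Even split, normal: 0.948 × 0.900 + 0.052 × 0.560 = 0.882.
- Even split, exact: 0.948 × 0.882 + 0.052 × 0.343 = 0.854.
- 80:20, normal: 0.747 × 0.900 + 0.253 × 0.560 = 0.814.
- 80:20, exact: 0.747 × 0.882 + 0.253 × 0.343 = 0.746.

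**The case against.** The strongest defence is that a redundancy rule is a reasonable choice here. The synopsis and section 1 state the aim as evaluating both tracers and name no MR comparator. The primary outcome in 10.1 compares all three methods. If one tracer adds nothing, sparing men further scans with two unapproved agents is defensible. All of this stands: the tracer comparison belongs to the study and the look itself is not at fault. What it leaves untouched is that a comparison with no test and no power ends the one that has both.

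A second objection is that the effect is small. At an even split it is, at two to three points of overall power. But the plan does not give the split or the unit of the 1/3, and other plausible values make the loss larger.

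Three stronger readings are tempting and are not supported.

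- A reader might take *outperform* to mean more lesions in total, which would make stopping likely (about 85% at an even split with one extra lesion per discordant patient). That reading sets the bracket aside, so it is no measure of the risk.
- A reader might infer inflated type I error. The rule does not test PET/MRI against MR, so the one-sided 5% is not inflated.
- A reader might infer that nothing governs the analysis after a stop. Sections 11.4 to 11.4.2 do not depend on reaching 50, and the 12-month chart review in 6.3 covers every participant. Only the loss of power and precision goes unaddressed.

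**Conclusion.** The concern holds as an unreconciled rule, and the sponsor should correct it. Section 11.3 can end the trial before its powered question is answered, and 11.5 does not allow for this. The likely cost is modest: about a 5% chance of stopping under the plan's own 1/3 with an even split. It could be as low as about 2% if some discordant patients have extra lesions on both tracers, and as high as 16% to 25% under the other assumptions shown. If a stop does occur, the MR comparison can still be analysed but is clearly underpowered across the whole range of discordance examined. Confidence is medium, because the discordance, the split, the unit of the 1/3, the independence of lesions, and the independence of stopping from the MR result are all assumptions. The documents do not show that stopping is probable or that the look is improper.

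**What to change.** Reconcile 11.3 with 10.1, 11.4.2 and 11.5.

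1. Keep the look at 20, but let a trigger end only the head-to-head tracer comparison, which is then reported descriptively. PET/MRI versus MR continues to the planned 50. The sponsor states which tracer or tracers are then compared with MR, decides whether the second scan continues, and reconciles the two-scan schedule in 2.5, 5.2, 7 and 11.2 with that decision.
2. If a whole-study stop is what is intended, restate the power in 11.5 to allow for it, with its assumptions, and say that PET/MRI versus MR is descriptive after a stop.
3. In either case, give *outperform* one meaning distinct from the first trigger. For example: across the 20 participants one tracer shows no lesion that the other misses, and the other shows at least one additional lesion. Without the second half, the wording is also met when all findings are identical.

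The cost is an amendment to 11.3 and 11.5, plus the schedule sections if the scans change. No interim test against MR is added, so there is no alpha to adjust and no wait for biopsy or the 12-month reference standard. The downside of option 1 is that up to 30 already planned participants (50 − 20) continue after a trigger. Their exposure is that given in 8.1: 5.85 to 9.75 mSv for one tracer and 3.15 to 5.25 mSv for the other, so 9.0 to 15.0 mSv if both scans are done.

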#### **11.4 Key variables**

Reference standard: disease status of a lesion will be defined by biopsy of suspicious lesions, when clinically feasible. 12-months clinical follow-up with imaging will be gold standard if biopsy cannot be done.

Test to be evaluated:  $^{68}\text{Ga}$ -NeoBOMB1 and  $^{68}\text{Ga}$ -PSMA R2 positivity will be determined by the operator as uptake more than the adjacent background (malignant) or less (benign). Visual conspicuity against background on the diffusion weighted images and presence of an anatomically corresponding abnormality on the T1w and T2w images are the criteria for detecting a lesion on MRI.

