## 2. BACKGROUND

### 2.1 Preliminary information

Data from the American Cancer Society suggests that prostate cancer (PC) will continue to be the leading non-cutaneous cancer diagnosis in males in 2016 in the US with 180,980 estimated new cases, and has the second highest mortality with 26,120 estimated deaths (1). Subsequent treatment is multifaceted and may involve observation, surgery (prostatectomy), radiation therapy (external beam or brachytherapy), hormonal therapy, chemotherapy, or a combination of these (2-4).

Up to 40% of the patients with prostate cancer develop biochemical recurrence within 10 years after initial treatment (5). Usually an increase of the PSA-level precedes a clinically detectable recurrence by months to years (6). However, it cannot differentiate between local, regional or systemic disease with the necessary precision that is essential for further disease management (7).

Morphological imaging methods exhibit considerable limitations: sensitivity ranges between 25% and 54% for the detection of local recurrence by transrectal ultrasound (TRUS) or contrast-enhanced CT and is moderately improved by using functional MRI techniques (7-9). The sensitivity for detection of lymph node metastases of CT or MRI is reported to be 30-80% (10). Ultra-small particles of iron oxides (USPIOs) proved to be very effective, but are yet to be approved by regulatory authorities (11). Bone metastases presenting as osteoblastic lesions can be effectively detected by bone scintigraphy, PET, CT and MRI (12,13).

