### **6.3. Follow-up**

Active subject participation ends after the 24 to 72 hour post-scan Safety Follow-up. Investigators will follow subjects by chart review for 12 months post-scan to record any standard of care biopsies or imaging results. If required by treating physicians for standard of care biopsies, the investigators will assist with identification of lesions that can be biopsied, based on Ga-NeoBOMB1 and/or Ga-PSMA-R2 PET/MRI findings.

If a subject transfers clinical care outside of Stanford Healthcare during the chart review clinical follow-up period, investigators will request permission to contact the treating physician to review medical records.

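### True PET-only lesions still unresolved at 12 months count as not malignant, which biases the secondary predictive value downward and may shrink the PET-versus-MR sensitivity contrast

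*Combined protocol and SAP*

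**What the plan says.** All places are in the combined protocol and SAP.

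- **Reference standard.** Section 11.4 uses biopsy where clinically feasible; otherwise "12-months clinical follow-up with imaging will be gold standard if biopsy cannot be done". Section 10.1 says the same: "The gold standard will be based on either biopsy or one-year follow-up with imaging".
- **Source of the follow-up.** Section 6.3: "Investigators will follow subjects by chart review for 12 months post-scan to record any standard of care biopsies or imaging results". It sets no schedule or modality, and no section says which finding confirms or refutes a lesion.
- **How many rest on it.** Section 11.5: "We expect approximately 70% of patients (~35) to have one or more PET-positive findings and approximately 1/3 to be biopsied". Roughly two thirds are therefore left to follow-up.
- **What conventional imaging can see.** Section 2.1 says "sensitivity ranges between 25% and 54% for the detection of local recurrence by transrectal ultrasound (TRUS) or contrast-enhanced CT" and gives 30-80% for nodal metastases on CT or MRI. It also says that PSA usually rises months to years before recurrence can be detected clinically.
- **Where the label is used.** The secondary outcome in Section 10.4 is the percentage of detected lesions confirmed malignant, for each imaging method. Section 11.4.2 estimates sensitivity, specificity and predictive values, and compares PET/MRI with MR by McNemar tests. Section 11.4.1 restricts the analysis set to lesions identified on the two PET/MRI scans.
- **Treatment.** Section 5.3 lets treating physicians act on the scan results. No rule covers lesions treated before 12 months.

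**The concern.** The denominator in Section 10.4 contains every detected lesion, but the numerator contains only those confirmed. A lesion that is truly malignant, was not biopsied, and is still neither confirmed nor refuted at 12 months therefore lowers the reported predictive value exactly as a false positive would.

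The error is unlikely to fall evenly. A lesion already visible on baseline MR should be easy to see again on later anatomical imaging. A lesion seen only on PET has to become visible within the year, in patients whom the title and Section 10.1 describe as having uninformative conventional imaging. The reference is thus weakest for the lesions the tracers are meant to find.

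If the accuracy analyses in Section 11.4.2 also treat unresolved lesions as non-malignant, those lesions leave the sensitivity comparison, where they would have favoured PET. They enter the specificity comparison as PET errors and MR successes.

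**Working it through.** **1. The plan's own figure.** Section 11.5 states 90% power for 40% (MR) versus 60% (PET), 50 units, one-sided 5%.

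- One-sample normal approximation: (0.20√50 − 1.645√0.24)/√0.24 = (1.414 − 0.806)/0.490 = 1.242, power 89.3%.
- Paired McNemar: power = Φ{[√n(b − c) − 1.645√(b + c)] / √[b + c − (b − c)²]}, where b is PET-only and c is MR-only. This gives 90.0% when b = 0.226 and c = 0.026, a discordance of about 0.25. The plan states no discordance. At 0.28 power is 86.7%; with independent reads (0.52) it is 62.9%.

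The stated power can be reproduced, but under the paired test it implies high overlap between reads.

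**2. Assumptions for the bias.** True sensitivities are 40% and 60% (Section 11.5). PET makes no false-positive calls. One third of PET-only lesions are biopsied, and biopsy is always right (Section 11.5's fraction describes patients, not lesions). MR-visible lesions are all confirmed. Unbiopsied PET-only lesions are confirmed with probability s = 0.25 to 0.54, which borrows the range in Section 2.1. The documents give no 12-month confirmation rate.

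Overall PET-only confirmation: k = 1/3 + (2/3)s, so k = 0.50 at s = 0.25 and 0.693 at s = 0.54.

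| Case | Both | PET-only | MR-only |
|---|---|---|---|
| Independent reads | 0.24 | 0.36 | 0.16 |
| High overlap (90% of MR lesions also on PET) | 0.36 | 0.24 | 0.04 |

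**3. Secondary predictive value.** Apparent PPV = (both + PET-only × k)/0.60; the true value is 100%.

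- Independent: (0.24 + 0.36 × 0.50)/0.60 = 70%; (0.24 + 0.36 × 0.693)/0.60 = 82%.
- High overlap: (0.36 + 0.24 × 0.50)/0.60 = 80%; (0.36 + 0.24 × 0.693)/0.60 = 88%.
- At s = 0.80, the top of the nodal range, k = 0.867 and PPV is 92% (independent) or 95% (high overlap).

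**4. Sensitivity contrast in the Section 11.4.1 set, if unresolved means non-malignant.** With PET taken as one test, its sensitivity is 100% by construction. The contrast is PET-only × k/(both + PET-only × k).

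- Independent: 0.36/0.60 = 60 points with perfect truth; 0.18/0.42 = 43 to 0.2496/0.4896 = 51 points observed.
- High overlap: 0.24/0.60 = 40 points with perfect truth; 0.12/0.48 = 25 to 0.1664/0.5264 = 32 points observed.

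**5. Dependence on the lesion set.** Take the cells that reproduce 90% power (both 0.374, PET-only 0.226, MR-only 0.026, neither 0.374). Let u = 1 − s be the unconfirmed share of true unbiopsied PET-only lesions, so k = 1 − (2/3)u. Contrast in points:

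| Lesion set | u = 0 | u = 0.5 | u = 1 |
|---|---|---|---|
| All true lesions, including those both reads miss | 20.0 | 13.5 | 5.8 |
| Lesions found by either read | 32.0 | 22.7 | 10.4 |
| PET-identified lesions (Section 11.4.1) | 37.6 | 28.7 | 16.7 |

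With 50 true lesions and the MR-only cell kept, McNemar power is 90%, 68% and 29% at these values of u. Within every set the contrast falls as u rises. Whether it falls below 20 points depends on the set and on u.

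**The case against.** The other side has several good points.

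- The primary outcome in Section 10.1, lesions detected per patient by each method, needs no reference standard. Nor do the two numbered expectations there about proportions of patients with lesions.
- The 25-54% describes transrectal ultrasound or contrast-enhanced CT for local recurrence. It is not a 12-month confirmation rate for all sites. Section 2.1 gives nodes up to 80% and says bone metastases are detected effectively.
- The lead time runs from PSA rise, not from the scan, and patients enter after biochemical recurrence, so part of it has already passed.
- Section 6.3 does not limit follow-up to anatomical imaging. It also lets PET findings help locate biopsy targets, which favours confirming them.
- Section 11.4 gives no scoring rule for unresolved lesions, so treating them as negative in the sensitivity analysis is an inference.
- Confirming every MR-visible lesion is generous to MR. With 80% confirmed, the independent-case contrast in step 4 becomes 0.18/0.372 = 48 to 0.2496/0.4416 = 57 points, a smaller loss. The same change lowers PPV further, to 0.372/0.60 = 62% to 0.4416/0.60 = 74%.

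These points limit the size of the effect. They do not remove the Section 10.4 arithmetic, which follows from its stated numerator and denominator.

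A reader might go further and infer that the observed contrast drops below the planned 20 points, so that a real advantage over MR is missed. With independent reads and every lesion from either read in the reference set, it would be only 3-14 points. The documents do not support that reading: it counts MR-only lesions that Section 11.4.1 excludes, and it needs a discordance (0.52) at which power is 63%, not 90%. Under Section 11.4.1 the contrast stays above 20 points over the assumed range.

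**Conclusion.** The concern holds for the secondary outcome. Section 10.4 as written counts true PET-only lesions unresolved at 12 months as not malignant, so the predictive value is biased downward. With no true false positives and 25-54% confirmation of unbiopsied PET-only lesions, the apparent PPV is about 70-88% across the two overlap cases. That range rests on an assumed confirmation rate and on applying the one-third biopsy fraction to lesions.

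For Section 11.4.2 the conclusion is conditional. If unresolved lesions are scored the same way, the sensitivity contrast shrinks relative to the same lesion set with perfect truth, by an amount the documents do not fix. A fall below 20 points is not established. The primary lesion count is unaffected. The change should be made, but the trial's main result does not depend on it.

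**What to change.** - **Section 11.4:** state what confirms and what refutes a lesion, and add an indeterminate class: no biopsy, and neither confirmed nor refuted by 12-month imaging. Include lesions treated in the interval.
- **Section 10.4:** report confirmed, benign and indeterminate counts separately for each method. Give PPV among classified lesions, then with all indeterminate lesions set to malignant, and again with all set to benign.
- **Section 11.4.2:** run the sensitivity and specificity McNemar comparisons under both extreme settings. Label sensitivity as relative to the lesions in the Section 11.4.1 set.

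The two extreme settings are the essential part for sensitivity. Dropping indeterminate lesions leaves the same confirmed-malignant set, and so the same contrast. In step 4 the two settings would give 43-51 and 60 points (independent), or 25-32 and 40 points (high overlap), and so show the reader how much rests on unresolved lesions.

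The cost is wording in three sections, recording interval treatment in the existing chart review, and extra analysis runs; no added scans are needed. The downside is fewer lesions with a definite label and a wider reported range.

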Various targets have been addressed by molecular imaging to improve the detection of recurrent prostate cancer. PET tracers such as  $^{18}\text{F}$ - or  $^{11}\text{C}$ -labeled choline and  $^{11}\text{C}$ -acetate have been investigated for the diagnosis of recurrent (14-16) prostate cancer. Their feasibility in primary diagnosis is limited because of uptake in benign tissue such as benign prostatic hyperplasia (BPH) or inflammatory lymph nodes (17,18). In addition, fluorinated versions are not available in the United States, while  $^{11}\text{C}$ -labeled tracers cannot be widely used due to the requirement for an on-site cyclotron due to the short half-life.  $^{18}\text{F}$ -FACBC, a new synthetic amino acid, might be superior when compared to  $^{11}\text{C}$ -choline PET/CT (19). However, recent work indicates that  $^{18}\text{F}$ -FACBC uptake in prostate cancer is similar to that in BPH nodules (20). Prostate-specific membrane antigen (PSMA) continues to elicit high interest. This cell surface protein is significantly overexpressed in prostate cancer cells when compared to other PSMA-expressing tissues such as kidney, proximal small intestine or salivary glands. It therefore provides a promising target for prostate cancer-specific imaging.

Recently methods have been developed to label PSMA ligands with  $^{68}\text{Ga}$  and  $^{18}\text{F}$ . Initial experience suggests that these novel tracers can detect prostate cancer relapses and

metastases with high contrast by binding to the extracellular domain of PSMA, followed by internalization (21,22). However, these promising agents do not detect all recurrences.

Consequently, improved imaging of biochemically recurrent prostate cancer continues to be an area of unmet clinical need.

Gastrin-releasing peptide receptors (GRPR) are highly overexpressed in several human tumors, including PC (23). GRP receptor was detected in 63-100 % of human prostate cancer tissue (24,25). Moreover, because of their low expression in BPH and inflammatory prostatic tissues (25), imaging of GRPR has potential advantages over current choline- and acetate-based radiotracers.

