### **10.4 Secondary Outcome Measure**

- Secondary Outcome measure: Predictive value of malignancy
- Timeframe: After 1 year clinical follow-up
- Description: The predictive value of Ga- NeoBOMB1 PET/MRI and Ga-PSMA R2 PET/MRI imaging will be evaluated based on biopsy and/or imaging results during 12 month standard clinical follow-up. Outcome will be reported as- percentage of detected lesions that were confirmed to be malignant for each imaging method.

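### For non-biopsied lesions the reference standard admits follow-up imaging that shares a target or modality with a test under study, with no required blinding, so predictive values and accuracy estimates can be biased

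*Combined protocol and SAP*

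**What the plan says.** Section 11.4 (Key variables) puts biopsy first: "disease status of a lesion will be defined by biopsy of suspicious lesions, when clinically feasible". Failing that, "12-months clinical follow-up with imaging will be gold standard if biopsy cannot be done". Section 10.1 presents the two as alternatives: "The gold standard will be based on either biopsy or one-year follow-up with imaging". In section 10.4 the predictive value "will be evaluated based on biopsy and/or imaging results during 12 month standard clinical follow-up". Section 6.3 says where the follow-up data come from: "Investigators will follow subjects by chart review for 12 months post-scan to record any standard of care biopsies or imaging results". The study calendar (section 7) lists chart review and no follow-up scan. None of these sections names the admissible modalities, excludes a tracer, or says what happens when biopsy and imaging disagree.

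Lesion truth is used in two places. The secondary outcome in 10.4 is the "percentage of detected lesions that were confirmed to be malignant for each imaging method". Section 11.4.2 adds: "Sensitivity, specificity, and positive and negative predictive value of imaging modalities will be estimated", with McNemar tests of PET/MRI against MR alone.

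The blinding in sections 5.3 and 10.2 covers the readers of the study scans. Nothing comparable covers whoever assigns truth. Study results go to the treating physicians (5.3), and investigators may use them to help identify lesions for biopsy (6.3).

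**The concern.** A reference standard should be independent of the tests it judges. A later PSMA-targeted PET shares its target with PSMA R2, so it tends to repeat that tracer's calls, right or wrong. It is also a poor judge of a lesion seen only on NeoBOMB1. Section 2.1 says of the existing PSMA tracers: "However, these promising agents do not detect all recurrences". A GRPR-targeted PET would create the mirror-image problem. Follow-up MRI would favour what MR had already shown, against lesions seen only on PET.

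The lesions most exposed are those on which the two tracers disagree. These are the ones that section 11.4.2 sets out to tabulate and explain. If truth is assigned with the detecting scan in view, the same lesions are open to a second, unquantified bias.

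**Working it through.** **Inputs from the documents.** Section 11.5: about 35 PET-positive men, about one third biopsied, about 50 lesions, sensitivity 60% for PET and 40% for MR, 90% power at one-sided 5%. Section 11.3: two thirds same and one third different findings, taken from another PSMA and bombesin tracer pair.

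**Assumptions.** The biopsy and discordance fractions, which read as per patient, apply per lesion. Discordance splits evenly, so 1/6 of lesions are seen by each tracer alone. The share *u* of non-biopsied lesions settled by PSMA PET is not in the documents and is varied from 0 to 1. All other verification is correct.

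**1. The plan's power figure.** Treating MR sensitivity as a fixed 40%: Φ(0.20 × √50 / √0.24 − 1.645) = Φ(1.242) = 89.3%, close to the stated 90%. It is not in dispute here and is used only to price the fix.

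**2. Lesions that rely on imaging.** If half of 35 men have a second lesion, there are 35 × 1.5 = 52.5 lesions. Of these, 52.5 × 2/3 = 35 are not biopsied and 17.5 are. With *u* = 25 to 50%, PSMA PET settles 8.75 to 17.5 lesions, about 9 to 18.

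**3. Predictive-value gap.** Let both tracers have true predictive value *t*, and let *q* = (2/3) × *u*. Of each tracer's lesions, (1/6)/(5/6) = 20% are seen by it alone. If the later PSMA PET repeats the PSMA R2 result exactly:

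- PSMA R2: (1 − *q*) × *t* + *q*
- NeoBOMB1: (1 − *q*) × *t* + 0.8 × *q*
- Gap: 0.2 × *q*, whatever *t* is

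With *t* = 90% for illustration:

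| *u* | *q* | PSMA R2 | NeoBOMB1 | Gap (points) |
|---|---|---|---|---|
| 0 | 0 | 90.0% | 90.0% | 0 |
| 25% | 1/6 | 91.7% | 88.3% | 3.3 |
| 50% | 1/3 | 93.3% | 86.7% | 6.7 |
| 100% | 2/3 | 96.7% | 83.3% | 13.3 |

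If the later PET repeats the earlier result 90% of the time, the gap is multiplied by 2 × 0.9 − 1 = 0.8, giving 2.7, 5.3 and 10.7 points. At full use, discordance of 20% or 50% in place of one third gives 7.4 or 22.2 points.

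**4. Sensitivity among PET-detected lesions.** Take 50 lesions: 33.3 seen by both tracers and 8.33 by each alone, 90% malignant. Both tracers truly have 83.3%. At full use, lesions called malignant number 33.3 × 0.967 = 32.2 (both), 8.33 × 0.967 = 8.06 (PSMA R2 only) and 8.33 × 0.9 × 1/3 = 2.5 (NeoBOMB1 only), 42.8 in all. PSMA R2 becomes 40.3/42.8 = 94.2%, and NeoBOMB1 34.7/42.8 = 81.2%. Only 2.5 of the 7.5 truly malignant NeoBOMB1-only lesions are called malignant.

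**5. Precision if lesions are set aside.** Removing 8.75 to 17.5 of 52.5 lesions leaves 43.75 to 35. The approximation in step 1 gives 77.9% at 35 lesions and 51.5% at 17, about the number biopsied.

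The documents give no basis for a similar figure for MRI used as reference.

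**The case against.** The strongest reply is that the mechanism is hypothetical. No section says that a PSMA- or GRPR-targeted PET will be done in follow-up. Section 6.3 limits the record to standard care, section 2.1 describes PSMA ligands as recent, and section 2.2 says neither study tracer is FDA-approved. This stands as a limit on size: with no such PET, the tracer gap is 0. It does not close the gap in the rule, because standard care does not exclude a same-target PET or an MRI.

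The arithmetic also stacks assumptions, and at 25 to 50% use the gap is smaller than the sampling error of one predictive value. At 90% with 43.75 lesions, that is 1.96 × √(0.09/43.75) = about ±9 points. This is fair, but the bias has a fixed direction, would not shrink with more lesions, and falls wholly on the discordant lesions.

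Section 11.4 already puts biopsy first, and the looser wording of 10.4 may only list data sources. That is a reasonable reading, so the inconsistency is minor.

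A reader might infer that PSMA R2 lesions will be confirmed and NeoBOMB1 lesions wrongly cleared. The documents leave this possible but do not show that it will happen, and a false-positive NeoBOMB1-only lesion would be cleared correctly. A reader might also infer a marked fall in NeoBOMB1 sensitivity. It falls only from 83.3% to 81.2% even at full use; the larger distortion is the PSMA R2 rise.

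**Conclusion.** The concern holds as a gap in the definition of lesion truth. For about two thirds of lesions, the plan admits imaging that shares a target with a study tracer or a modality with the comparator, and does not blind the person who assigns truth. If such imaging is used, predictive value (10.4) and the estimates in 11.4.2 are biased toward the related test.

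The artificial predictive-value gap between equally accurate tracers is 0 with no PSMA PET, about 3 to 7 points at 25 to 50% use, and about 13 points at full use. This rests on one third biopsied and one third discordance applied per lesion, an even split, and a repeatable PSMA PET. The use range is an assumption.

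The reach is limited. The primary outcome in 10.1, lesions detected per patient, needs no reference standard. Section 11.4.2 plans no formal test of one tracer against the other, so the tracer gap affects descriptive estimates. A reader might conclude that same-target PET should be barred outright. The documents do not support that as a clear gain: about 9 to 18 lesions could become unverified under the assumed use, and relying on MRI instead would let the comparator settle truth.

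**What to change.** - **One hierarchy.** State the same rule in 10.1, 10.4 and 11.4: biopsy first, imaging only where there is no biopsy.
- **Record the source.** For each lesion, capture the confirming modality and, for PET, the tracer.
- **Blind the assignment as far as feasible.** Have the existing reviewers assign truth by lesion location without being shown which study scan detected it. Because results are released to treating physicians, charts may reveal this, so full blinding cannot be promised.
- **Report three sets of estimates** of predictive value, sensitivity and specificity: all verified lesions; excluding lesions settled only by a PET with the same target as a study tracer (and, for PET/MRI against MR, those settled only by MRI); and biopsied lesions only.

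The cost is wording in three sections, one extra case-report field, and less precise restricted analyses: possibly 9 to 18 fewer lesions in the second set before any MRI exclusion, and about 17 lesions in the third. No study procedure is added. The field and the rule should be in place before truth is assigned, because otherwise independent and same-target confirmation may not be separable later.
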